A phase 1 dose escalation study (C15003) of MLN4924 (pevonedistat) treated patients with acute myelogenous leukemia, high-grade myelodysplastic syndrome or acute lymphoblastic leukemia on 4 different dosing schedules (Schedule A: Days 1, 3, and 5 at starting dose 25 mg/m²; Schedule B: Days 1, 4, 8 and 11 at starting dose 147 mg/m²; Schedule C: Days 1, 8, and 15 at starting dose 44 mg/m²; Schedule D: [MLN4924 (pevonedistat) starting dose of 45 mg/m² and azacytidine dose of 75 mg/m²] Cycle 1: Days 1, 4, 11 and 15, with azacytidine on Days 8-12 and 15-16 of a 35-day cycle, Cycles 2+: Days 1, 4, 8, and 11, with azacytidine on Days 1-5 and 8-9 of a 28-day cycle; Schedule E: Days 1, 3, and 5, expansion cohort at a fixed dose of 50 mg/m²). A total of 72 patients were treated and DLTs observed included elevated LFTs, hypotension, cardiac failure, GI necrosis, lactic acidosis, myocardial ischemia, renal failure and rash morbilliform. The MTD was established at 59 mg/m² for Schedule A and 83 mg/m² for Schedule B. The MTD was not determined for Schedules C-E.

A phase 1 study (C15005) assessing MLN4924 (pevonedistat) in adult patients with melanoma administered MLN4924 (pevonedistat) in 2 dosing schedules; Schedule A: Days 1, 4, 8, and 11 at starting dose of 50 mg/m² and Schedule B: Days 1, 8, and 15 at starting dose 157 mg/m². Cycles were repeated every 21 days. A total of 37 patients were treated but the study was closed early by the study sponsor. DLTs observed included hypophosphatemia, elevated creatinine, myocarditis, acute renal failure, and hyperbilirubinemia. The MTD determined for Schedule A was 209 mg/m² and the MTD was not determined for Schedule B.

A phase 1b dose escalation study (C15009) of MLN4924 (pevonedistat) plus azacitidine in naïve patients with acute myelogenous leukemia assessed safety and tolerability of the drug combination. Patients were dosed with (MLN4924) pevonedistat on Days 1, 3, and 5 at a starting dose of 20 mg/m² and azacitidine on Days 1-5, 8, and 9 at 75 mg/m². Cycles were repeated every 28-days. A total of 64 patients were treated and responses of CR, CRi and PR were observed in 58% of patients. The overall response rate in evaluable patients was 58% with a median response duration of 8.3 months. Responses were identified in all cytogenetic risk groups, *TP53* mutations, low and high marrow blast counts and in *de novo* as well as secondary AML.

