6.2 Definition of Dose-Limiting Toxicity

AEs will be assessed according to the NCI Common Terminology Criteria for Adverse Events

(CTCAE), version 5.0. AEs possibly, probably, or definitely related to study drugs will be scored as toxicities.

All participating sites are expected to notify the Principal Investigator and Study Coordinator within 24 hours of awareness that a DLT has occurred.

• [REDACTED]

DLTs will be defined in Cycle 1 as any of the following events that are considered by the investigator to be related to therapy with MLN4924 (pevonedistat) and/or belinostat:

- Any grade 3 or greater non-hematological toxicity that does not recover within 1 week to grade ≤ 1 or baseline with optimal medical management, with the following exception :
 - Grade 3 hypophosphatemia
- Grade 3 or greater ECG QT corrected interval prolonged.
- Grade 3 or greater increased prothrombin time/international normalized ratio (PT/INR) or activated partial thromboplastin time (aPTT) in the absence of anticoagulation therapy.
- Grade 2 or greater elevation of the PT/INR or aPTT that is associated with clinically significant bleeding (CNS, GI, *etc.*).
- Grade 2 or greater increased AST, ALT or bilirubin that persists longer than 2 days between MLN4924 (pevonedistat) doses.
- Delayed initiation of Cycle 2 as follows:
 - More than 2 week delay due to lack of recovery (to $<$ Grade 1 or baseline) from treatment-related non-hematologic toxicity.
 - More than 4 week delay due to lack of recovery (to $<$ Grade 1 or baseline) from treatment-related hematologic toxicity believed not related to leukemic infiltration. Note: Bone marrow evaluation may be required.
- Grade 4 neutropenia or thrombocytopenia extending beyond day 42 in patients with less than 5% blasts in marrow, absence of MDS changes and/or absence of disease by flow cytometry in the marrow.
- Any toxicity that requires discontinuation of either study drug.
- Grade 3 or greater nausea or vomiting despite use of optimal anti-emetic prophylaxis. Optimal anti-emetic prophylaxis is defined as an anti-emetic regimen that employs a 5-hydroxytryptamine 3 serotonin receptor antagonist given in standard doses and according to standard schedules.
- Grade 3 or greater diarrhea that occurs despite maximal supportive therapy
- Grade 3 arthralgia or myalgia despite the use of optimal analgesia

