Supportive Care Guidelines

Condition	Recommendation
Antidiarrheal Therapy	Diarrhea can occur with belinostat. Study treatment-related diarrhea should be treated with loperamide 4 mg by mouth followed by 2 mg by mouth after each subsequent loose stool up to a maximum of 16 mg daily. Use alternate approaches (such as diphenoxylate-atropine) in patients intolerant of loperamide. Prophylactic loperamide should be considered in patients who have required therapeutic loperamide previously.
Electrolyte Abnormalities	Chemistry tests, including serum electrolytes, creatinine, magnesium, and calcium should be obtained prior to each cycle of therapy. Due to risks of QT prolongation, if hypokalemia and/or hypomagnesemia are present prior to administration of study drug, replete electrolyte(s) before proceeding with treatment. Monitor potassium and magnesium more frequently in symptomatic patients (e.g. , patients with nausea, vomiting, diarrhea, fluid imbalance, or cardiac symptoms).
Anemia and Thrombocytopenia	Belinostat can cause thrombocytopenia and anemia. Transfusion of packed RBCs and platelets is recommended per institutional guidelines.
TLS	While TLS is not expected, TLS labs will be performed on Days 1 through 3 of Cycle 1. Additional monitoring, prophylaxis and treatment for TLS is recommended in accordance with published guidelines (Jones et al. , 2015). Urinary alkalinization is not recommended.
Anti-infective Prophylaxis	Serious and sometimes fatal infections, including pneumonia and sepsis, have occurred with belinostat. Patients who are or are anticipated to become neutropenic should receive appropriate antimicrobial prophylaxis against bacteria, fungi, and herpes viruses in accordance with published guidelines (Taplitz et al. , 2018). Recommendation to use ciprofloxacin 500 mg orally BID. Anti-infective therapies can have potential for QT prolongation and CYP450 interactions.

QTc=Heart-rate corrected QT interval, ECG=Electrocardiogram, RBCs=Red Blood Cells, TLS=Tumor Lysis Syndrome, PTCL=Peripheral T-cell Lymphoma. BID=Twice a day.

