Pre-Syncope	2	
 Omit belinostat (if only belinostat due); or delay both agents (if both agents due).^{E, F} Obtain ECG for cardiology review/consultation; IF ECG shows new dysrhythmia or QTc grade ≥ 2 (>480 ms): 
 Consider hospitalization for monitoring with cardiology consultation. Follow instructions above for grade 3 QTc interval. For recurrent grade 2 pre-syncope or grade 3 syncope thought to be related to belinostat, discontinue protocol therapy. 	
 Delay both agents.^{E, F} Obtain ECG for cardiology review/consultation; IF ECG shows new dysrhythmia or QTc grade ≥ 2 (>480 ms): 
 Consider hospitalization for monitoring with cardiology consultation. Follow instructions above for grade 3 QTc interval. For recurrent grade 2 pre-syncope or grade 3 syncope thought to be related to MLN4924 (pevonedistat), consider discontinuation of protocol therapy.
Syncope	3		
Hypophosphatemia	3	
 Omit belinostat (if only belinostat due); or delay both agents (if both agents due).^{E, F} When toxicity resolves to grade ≤ 1 or tolerable grade 2, resume treatment with one dose-reduction step for belinostat. 	
 Delay both agents.^{E, F} When toxicity resolves to grade ≤ 1 or tolerable grade 2, resume treatment with one dose-reduction step for MLN4924 (pevonedistat).
	4		

Toxicity	Grade (CTCAE v5.0)	Modification of Belinostat ^{A, B}	Modification of MLN4924 (pevonedistat) ^{A, B, C}
All Other Non-Hematologic Toxicities ^G	2	Reduce belinostat by one dose-reduction step for any grade 2 toxicity that is intolerable or unresponsive to optimal management.	Reduce MLN4924 (pevonedistat) by one dose-reduction step for any grade 2 toxicity that is intolerable or unresponsive to optimal management.

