																		

- A. MLN4924 (pevonedistat): Dose as assigned; IV over 60 minutes (\pm 10 minutes) once daily (QD) on Days 1, 3, and 5 of each 21-day cycle. When both drugs are given on the same day (Days 1, 3, 5), start the MLN4924 (pevonedistat) infusion within 60 mins after the completion of belinostat infusion.
- B. Belinostat: Dose as assigned; IV over 30 minutes QD on Days 1-5 of each 21-day cycle. Infusion may be extended to 3 hours pending patient tolerance.
- Prior to treatment
 - Unless stated otherwise, baseline evaluations are to be conducted within 1 week prior to start of study therapy. Repeat if not within 1 week prior to Cycle 1, Day 1. In the event that the patient's condition is deteriorating, laboratory evaluations should be repeated within 48 hrs prior to initiation of the next cycle of therapy.
 - End of treatment visit occurs after completion of all study treatment.
 - See Section 6.8.
 - Only for patients with a CR, CRi, CRc, CRm, ML-FS, PR, or SD, capture reported clinical status approximately every 2 months for 2 years following end of safety follow-up until disease progression or death. See Section 6.8.
 - Urinalysis to include turbidity and color, pH, specific gravity, protein, ketones, bilirubin, occult blood, nitrite, glucose, and leukocyte esterase. Microscopic analysis should be done at the discretion of the treating physician.
 - Include over-the-counter medications.
 - Sodium, potassium, carbon dioxide content, chloride, creatinine, blood urea nitrogen (BUN), glucose and calcium.
 - Alkaline phosphatase, ALT, AST and total bilirubin assessments must be performed and read prior to each dose of MLN4924 (pevonedistat).
 - Total bilirubin, direct bilirubin, ALP (alkaline phosphatase), AST, ALT, total protein, albumin.
 - Hepatitis serologies and, if needed, HBV viral load testing are to be done \leq 4 weeks prior to the start of therapy. HBV viral load only necessary if patients are Hepatitis B Ab positive.
 - Pre- & post-treatment on Cycle 1 Day 4 and whenever clinically indicated. Patients with risk factors for QT prolongation including CHF, bradyarrhythmias, electrolyte abnormalities or those on other drugs known to prolong the QT/QTc interval, such as Class Ia and III anti-arrhythmics, should be closely monitored as clinically indicated with ECGs and serum electrolytes (magnesium, potassium) while on study treatment. See Section 6.5.

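### Phosphate is not scheduled after Cycle 1 Day 3, so from Day 4 onward the hypophosphatemia dose-modification and DLT criteria cannot be applied systematically from scheduled tests

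*Combined protocol and SAP*

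**What the plan says.** **Rules that use phosphate.** The Section 7.2.2 table has a row headed "Hypophosphatemia" covering grades 3 and 4. It calls for belinostat to be omitted or both agents delayed, for resolution to grade 1 or less or a tolerable grade 2, and for resumption one dose-reduction step lower. Nothing in the row limits it to Cycle 1. Section 7.3 makes a new cycle conditional on related toxicity having resolved to grade 1 or less, to baseline, or to a level accepted after discussion with the principal investigator.

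The first DLT bullet in Section 6.2 is "Any grade 3 or greater non-hematological toxicity that does not recover within 1 week to grade ≤ 1 or baseline with optimal medical management", with one named exception, "Grade 3 hypophosphatemia". Grade 4 is not excepted. Other bullets (delayed Cycle 2, discontinuation of either drug, and pevonedistat-related grade 2 or greater toxicity that the investigator judges to need a dose reduction) could also be reached.

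**Measurements scheduled.** The Section 11 row for LDH and PO4 is marked at baseline and Cycle 1 Days 1, 2 and 3 only. Footnote h defines the basic metabolic panel as "Sodium, potassium, carbon dioxide content, chloride, creatinine, blood urea nitrogen (BUN), glucose and calcium". The hepatic panel is "Total bilirubin, direct bilirubin, ALP (alkaline phosphatase), AST, ALT, total protein, albumin". Section 6.5 adds that "TLS labs will be performed on Days 1 through 3 of Cycle 1" and that "Chemistry tests, including serum electrolytes, creatinine, magnesium, and calcium should be obtained prior to each cycle of therapy".

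**Background.** Section 2.2.2.2 reports for a melanoma study of pevonedistat that "DLTs observed included hypophosphatemia, elevated creatinine, myocarditis" and others. Section 10.1.1.1 lists hypophosphatemia as possibly related to pevonedistat, in the column for frequencies of 20% or less.

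**The concern.** The plan writes specific actions for hypophosphatemia, but its calendar stops measuring phosphate before the last pevonedistat dose of Cycle 1 and does not resume. A site that follows the calendar exactly has no scheduled value to tell it whether the Section 7.2.2 row applies, whether an event has resolved enough to resume or start a cycle, or whether a Cycle 1 event is exempt (grade 3) or may count as a DLT (grade 4 without recovery).

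What is at stake is completeness and comparability. Sites that order phosphate by habit will find and act on events that other sites do not see. Recorded hypophosphatemia rates, dose reductions and, less often, DLT classification would then depend partly on local practice.

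**Working it through.** The plan states no figure on this point, so there is none to reproduce. The check sets the Section 11 marks against dosing days and the times at which the rules need a value.

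| Day | Pevonedistat | Belinostat | Basic metabolic panel | Phosphate |
|---|---|---|---|---|
| C1 D1 | yes | yes | yes | yes |
| C1 D2 | no | yes | yes | yes |
| C1 D3 | yes | yes | yes | yes |
| C1 D4 | no | yes | no | no |
| C1 D5 | yes | yes | yes | no |
| C1 D8, D15 | no | no | yes | no |
| Later D1, D3, D5 | yes | yes | yes | no |
| Later D2, D4 | no | yes | no | no |

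**1. Is the column reading sound?** Tables in the source may be broken, so the four marks need support. The Section 6.5 statement that tumor lysis labs are done on Cycle 1 Days 1 through 3 matches them. The neighbouring uric acid and magnesium row continues to Days 5, 8 and 15 and to Day 1 of later cycles, while the LDH and PO4 row does not.

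**2. Does another panel supply phosphate?** Footnote h names 8 analytes and the hepatic panel names 7. Phosphate is in neither.

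**3. Coverage in Cycle 1.** Phosphate falls on 2 of 3 pevonedistat days (1 and 3), 3 of 5 belinostat days (1 to 3), and 3 of the 6 metabolic-panel days (1, 2, 3, 5, 8, 15). The three draws without it are Days 5, 8 and 15. The calendar does not say for this row whether blood is taken before or after dosing. If before, the Day 3 value reflects one pevonedistat dose; if after, two. Either way, none follows the third.

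**4. Coverage in later cycles.** 0 of 3 pevonedistat days, 0 of 5 belinostat days, 0 of 3 metabolic-panel days.

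**5. The 1-week recovery test.** Counting 7 days from a first abnormal value:
- Day 2: 2 + 7 = Day 9.
- Day 3: 3 + 7 = Day 10.
- Day 1, only if drawn after dosing: 1 + 7 = Day 8.

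No scheduled phosphate lies between Day 4 and Day 10, so neither recovery after Day 3 nor its absence can be established from scheduled tests.

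**6. Consistency among the rules.** Footnote G to the Section 7.2.2 table says modification is not required for asymptomatic laboratory abnormalities and excepts only AST, ALT and bilirubin. Its mark sits on the row for all other toxicities, not on the hypophosphatemia row, so its reach is unclear. Separately, grade 3 hypophosphatemia is exempt under the first DLT bullet, yet Section 7.2.2 prescribes a dose-reduction step for it. The DLT bullet on toxicity needing a pevonedistat reduction could therefore bring it back. These texts must be reconciled with each other as well as with the calendar.

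**The case against.** A reader might infer that the hypophosphatemia rules cannot be applied at all. The documents do not support that. Day 1-3 values are available, AE assessment runs through treatment, and all AEs must be reported (Section 10.4). When dosing is delayed, Section 7.2.1 requires regular re-evaluation for resumption up to Day 12. For an event found by Day 3, that can cover the recovery period. This stands, but re-evaluation starts only once an event has been found and does not name phosphate. It is not triggered by an event arising after the Day 5 doses, when no dose is due in that cycle.

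A reader might also infer that hypophosphatemia drives DLT decisions. It does not: Section 6.2 names it only as an exemption, and the direct route left is related grade 4 without recovery.

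Other points have weight:
- If footnote G governs the hypophosphatemia row, routine detection of asymptomatic low values would seldom change dosing. Its placement leaves this open.
- The pre-cycle sentence in Section 6.5 is not exhaustive, and a site could read phosphate into serum electrolytes. It names magnesium and calcium but not phosphate, and even on that reading Cycle 1 Days 4 to 21 remain uncovered.
- The documents do not reproduce the CTCAE grade definitions, so whether a laboratory value alone fixes the grade cannot be checked here.
- The earlier DLT came from a melanoma study on other schedules, with an MTD of 209 mg/m² on one of them. The DLT lists given for C15001 and C15003, which included Days 1, 3 and 5 schedules, do not name hypophosphatemia. The precedent shows that the event can occur, not how often it will here.
- Counting calendar days exaggerates the gap. Phosphate is absent on 21 − 3 = 18 of 21 days, but by the same count the metabolic panel is absent on 21 − 6 = 15.

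**Conclusion.** The inconsistency holds, and it is modest. From Cycle 1 Day 4 onward, including after the Day 5 pevonedistat dose and in all later cycles, the grade 3/4 modification, resumption, new-cycle and 1-week recovery criteria cannot be applied systematically from scheduled assessments. The useful measure is 3 Cycle 1 chemistry draws without phosphate (Days 5, 8 and 15) and no scheduled phosphate in later cycles.

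This rests on the calendar row being read correctly, which the tumor lysis sentence supports, and on a phosphate measurement being needed to recognise the event. It does not show that the toxicity will be understated by any particular amount. The documents give no event rate for this combination, and unscheduled testing may fill part of the gap. The escalation rules and sample size are not affected.

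**What to change.** Reconcile the Section 11 calendar and its panel footnotes, and the pre-cycle electrolytes sentence in Section 6.5, with the hypophosphatemia row and footnote G in Section 7.2.2 and with the DLT bullets in Section 6.2. State which assessments feed each rule, so that the calendar supplies the measurement the rules use. Say whether footnote G reaches the hypophosphatemia row, and how the grade 3 exemption relates to the dose-reduction DLT bullet.

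If the rules are meant to be applied systematically, phosphate can be run on chemistry draws already scheduled: Cycle 1 Days 5, 8 and 15, and Day 1 of later cycles. The cost is one more analyte and some additional low-grade laboratory AEs to record, with no new visit or procedure. If reliance on clinically prompted testing is intended, the protocol should say so, so that sites act alike and recorded rates are read accordingly. No dose or clinical rule is proposed here.

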- Other grade 2 or greater MLN4924 (pevonedistat)-related non-hematologic toxicities that, in the opinion of the investigator, require a dose reduction or permanent discontinuation of MLN4924 (pevonedistat).

Note that hematologic toxicities are not DLTs except as noted above.

Only DLTs occurring during Cycle 1 will influence decisions regarding dose escalation, expansion of a dose level, or evaluation of intermediate dose levels. Patients will be monitored through all cycles of therapy for treatment-related toxicities.

Patients who for any reason are not evaluable for DLT will be replaced. See Section 9.3.1 for DLT Evaluable Population.

Management and dose modifications for AEs are outlined in Section 7.

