7.2 Dose Modifications

7.2.1 General Guidelines

- AEs will be identified and graded according to the NCI CTCAE v5.0. AEs that are not study drug-related (*e.g.*, disease-related AEs) do not require dose modification. Dose modification for non-study drug-related AEs is generally discouraged but permitted at investigator discretion.
- *Dose Modification for Hematology Toxicities:* There is no dose-modification for hematologic toxicity; however, in cases of non-disease related myelosuppression and when clinically indicated, dose modification will require discussion with PI.
- Dose reduction steps are shown in Section 7.1. Dose modification instructions for both agents are outlined in Section 7.2. Details regarding initiation of new cycles, resumption of treatment within a cycle and dose re-escalation are shown in Sections 7.3, 7.4 and 7.5, respectively.
- Dose modifications (including dose omission, dose reduction, and delays) will be based on the investigator's assessment of the relationship of the toxicity to each of the study drugs.
 - Belinostat should be modified only for AEs thought to be related to belinostat

- MLN4924 (pevonedistat) should be modified only for AEs thought to be related to MLN4924 (pevonedistat)
- If the AE could be related to both drugs or if the relationship of the AE is unclear, both study drugs should be modified.
- If a patient experiences several AEs and there are conflicting recommendations for dose modification, the investigator should observe the more cautious modification recommendation. Treatment Delays and Omissions:
 - At the beginning of a cycle:
 - All treatment-related toxicities must be resolved to \leq grade 1 for initiation of a new cycle (see Section 7.3).
 - Initiation of a new cycle occurs when both agents meet criteria to be given.
 - Delay in initiation of a new cycle by > 14 days requires discontinuation of study therapy.
 - Within a cycle:
 - **On days when only belinostat is due, if treatment criteria aren't met due to toxicity, then the belinostat dose scheduled on that date will be omitted and not made up** on a later date. When belinostat is omitted, patients should be assessed to determine if dosing may resume on the next scheduled dosing day.

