	3	
 Omit belinostat (if only belinostat due); or delay both agents (if both agents due). When toxicity resolves to grade ≤ 1 or tolerable grade 2, ^{E, F} resume treatment with one dose-reduction step for belinostat. If grade 3 toxicity recurs following belinostat dose reduction, omit belinostat (if only belinostat due); or delay both agents (if both agents due). When toxicity resolves to grade ≤ 1 or tolerable grade 2, ^{E, F} resume treatment with one dose-reduction step for both drugs 	
 Delay both agents. When toxicity resolves to grade ≤ 1 or tolerable grade 2, ^{E, F} resume treatment with one dose-reduction step for MLN4924 (pevonedistat). If grade 3 toxicity recurs following MLN4924 (pevonedistat) dose reduction, delay both agents. When toxicity resolves to grade ≤ 1 or tolerable grade 2, ^{E, F} resume treatment with one dose-reduction step for both drugs
	4	
 Omit belinostat (if only belinostat due); or delay both agents (if both agents due). When toxicity resolves to grade < 2, ^{E, F} resume treatment with one dose-reduction step for both drugs If grade 4 toxicity recurs following dose reduction, discontinue protocol therapy 	
 Delay both agents. When toxicity resolves to grade < 2, ^{E, F} resume treatment with one dose-reduction step for both drugs If grade 4 toxicity recurs following dose reduction, discontinue protocol therapy

Toxicity	Grade (CTCAE v5.0)	Modification of Belinostat ^{A, B}	Modification of MLN4924 (pevonedistat) ^{A, B, C}
Table Footnotes			

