
A. Refer to the General Guidelines in Section 7.2.1 All treatment related toxicities must be resolved to \leq grade 1 for initiation of a new cycle (see Section 7.3).
 
B. On days when only belinostat is due, if treatment criteria aren't met due to toxicity, the belinostat dose scheduled on that date will be omitted and not made up on a later date, with assessment to resume treatment done on the next scheduled dosing day. On days when both study agents are due, if treatment criteria aren't met for both agents, then both agents will be delayed and the schedule shifted to accommodate for the delay. Assessment to resume treatment will be done regularly to determine if dosing may resume, with a goal of delivering as much of the regimen as possible on or before Day 12.
 
C. For MLN4924 (pevonedistat), a minimum of 1 full calendar day between any 2 doses should be maintained, and a maximum of 3 doses of MLN4924 (pevonedistat) within the cycle must not be exceeded.
 
D. There are no dose modifications for grade 1 toxicity. For grade 2 toxicity, the dose of the study drug(s) may be reduced by one dose-reduction step at the investigator's discretion.
 
E. Within a cycle, if treatment is delayed, treatment must be resumed no later than Day 12; and all dosing for a cycle must be completed on or before Day 12.
 
F. If toxicity has not resolved after 14 days of treatment delay, protocol therapy will be discontinued.
 
G. Dose modifications are not required for asymptomatic laboratory abnormalities (other than increased AST, ALT, and bilirubin, for which dose modifications are listed on the table above).
			

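### Footnote G to the 7.2.2 table lifts the hold for asymptomatic laboratory abnormalities of any grade, so no rule requires withholding the remaining in-cycle doses for a related, asymptomatic grade 3-4 creatinine rise

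*Combined protocol and SAP*

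**What the plan says.** The Section 7.2.2 table has rows for gastrointestinal toxicity, fatigue, AST/ALT, bilirubin, QTc, pre-syncope and syncope, and hypophosphatemia. Everything else falls under "All Other Non-Hematologic Toxicities". For grade 3 and grade 4 events the belinostat column of that row reads "Omit belinostat (if only belinostat due); or delay both agents (if both agents due"), and the pevonedistat column delays both agents. Dosing resumes at grade 1 or less or a tolerable grade 2 after a grade 3 event, and below grade 2 after a grade 4 event.

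Footnote G is attached to that row label: "Dose modifications are not required for asymptomatic laboratory abnormalities (other than increased AST, ALT, and bilirubin"). Section 7.2.1 fixes the scope of the term: "Dose modifications (including dose omission, dose reduction, and delays) will be based on" the investigator's view of which drug caused the toxicity. The sentence introducing the 7.2.2 table defines the term in the same way.

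The study calendar (Section 11) places creatinine in the basic metabolic panel on Cycle 1 Days 1, 2, 3, 5, 8 and 15. In later cycles it is on Days 1, 3 and 5, marked as drawn before treatment. Only the liver tests must be performed and read before each pevonedistat dose.

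**The concern.** Because modification includes omission and delay, footnote G removes the requirement to hold as well as the requirement to reduce, and it does so at every grade. A patient whose creatinine reaches grade 3 or 4 early in a cycle, without symptoms, can be given the remaining doses of both drugs without departing from the protocol.

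The issue is patient safety within the cycle. Section 10.1 lists increased creatinine as possibly related to each drug. Section 2.2.2.2 lists elevated creatinine among the DLTs of two earlier pevonedistat studies (C15001 and C15005). Section 2.3 says that the two drugs had not been combined in humans before.

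The table is also uneven. Grade 3 hypophosphatemia, which Section 6.2 exempts from the general non-hematologic DLT criterion, has its own row requiring omission or delay. An asymptomatic grade 4 creatinine rise has no mandatory hold.

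**Working it through.** The plan gives no figure to reproduce. The check is a trace through the text, followed by a count of doses.

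**1. Does another rule restore the hold?**

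- Footnote A and Section 7.3 require recovery before a new cycle starts. They do not act within a cycle.
- Section 7.4 adds only dose spacing and the maximum number of doses.
- Section 7.2.1 and footnote B refer to treatment criteria, but these are not defined apart from the table.
- The rule in 7.2.1 favoring the more cautious recommendation covers several adverse events with conflicting advice, not a row and its own footnote.
- The supportive-care table in Section 6.5 says "Chemistry tests, including serum electrolytes, creatinine, magnesium, and calcium should be obtained prior to each cycle of therapy". It requires action only on low potassium or magnesium.
- Section 6.2 counts "Any grade 3 or greater non-hematological toxicity that does not recover within 1 week to grade" 1 or baseline. This classifies the event and does not direct dosing. The earliest it can be met is onset + 7 days: Day 1 gives Day 8, Day 3 gives Day 10, Day 5 gives Day 12. All fall after planned dosing ends on Day 5. In addition, "Only DLTs occurring during Cycle 1 will influence decisions regarding dose escalation", so it has no role in later cycles.

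The first mandatory gate is therefore the start of the next cycle.

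**2. Doses still to be given.** Pevonedistat is given on Days 1, 3 and 5 and belinostat on Days 1-5. If the result is read before that day's dose, count doses on or after the result day. If it is read afterwards, count doses after that day.

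| Cycle 1 result day | Read before dose (pevonedistat; belinostat) | Read after dose |
|---|---|---|
| 2 | 2/3; 4/5 | 2/3; 3/5 |
| 3 | 2/3; 3/5 | 1/3; 2/5 |
| 5 | 1/3; 1/5 | none |

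The read-after column applies because the Cycle 1 panels carry no before-treatment mark in the available text, where a lost superscript is possible. In later cycles the panel is drawn before treatment, so the exposure is up to 2/3 and 3/5 on Day 3, and 1/3 and 1/5 on Day 5.

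**3. Coagulation.** Section 6.2 makes "Grade 3 or greater increased prothrombin time/international normalized ratio (PT/INR) or activated partial thromboplastin time (aPTT") without anticoagulation a DLT with no symptom condition, yet footnote G waives the hold. In Cycle 1 these tests fall on Days 1, 5, 8 and 15, so Day 5 is the only planned dosing day with a result after treatment has begun: 1/3 and 1/5 if read first, none if read after. Doses shifted as late as Day 12 could add to this. In later cycles the test is on Day 1 only, where the new-cycle rule applies.

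**4. Would a mandatory hold cost DLT evaluability?** Section 9.3.1 needs at least 2/3 pevonedistat and 4/5 belinostat. Apply the existing mechanics: belinostat-only doses are omitted, two-drug days shift, pevonedistat doses are separated by a full day, and nothing is given after Day 12. For one creatinine episode in Cycle 1 there are 3 result days x 2 reading times x 7 recovery days (onset + 1 to onset + 7) = 42 cases. Delivered totals (pevonedistat, belinostat) are:

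- Day 2: 3, 4 (read before) or 3, 5 (read after).
- Day 3: 3, 5 (read before); 3, 4 or 3, 5 (read after).
- Day 5: 3, 5 either way.

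All 42 meet 9.3.1. With recovery at onset + 8, the lowest total is 2, 4, which is still evaluable. An episode not back to grade 1 or less or baseline within a week is a DLT, and that patient is evaluable by definition.

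If dosing is not resumed in the cycle and there is no DLT, the totals are 1, 1 or 1, 2 for Day 2, and 1, 2 or 2, 3 for Day 3. None of these is evaluable. A Day 5 hold leaves 2, 4, which is evaluable. A second omitted belinostat-only dose leaves 3/5 belinostat, which is not.

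**5. Interaction with footnote F.** Footnote F ends protocol therapy if toxicity persists after 14 days of treatment delay. A mandatory Day 3 hold could start that clock at once: 3 + 14 = Day 17. Without the hold, Section 7.3 allows 14 days from the planned Day 22 start: 22 + 14 = Day 36.

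**The case against.** The strongest reply is that the footnote is deliberate and permissive. The authors dealt with AST/ALT, bilirubin and hypophosphatemia in their own rows, require potassium and magnesium repletion, and leave other asymptomatic values to judgement. Section 6.7 lets the investigator stop treatment for unacceptable adverse events or in the patient's interest. Tumor lysis laboratory tests are done on Cycle 1 Days 1-3, DLTs must be notified within 24 hours, and safety data are monitored as they are entered. All of this stands and bears on the size of the problem, but none of it requires a hold.

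The event is also narrow: related, grade 3-4, asymptomatic, recorded only as a laboratory value, and found while doses remain. Entry requires normal creatinine clearance or an eGFR of at least 60 mL/min/1.73 m². This too stands.

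Three stronger readings are tempting and not supported:

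- *That the protocol directs dosing to continue.* It does not. A modification that is not required remains allowed.
- *That DLT counts or the MTD are biased.* Footnote G does not enter the Section 6.2 criteria, and an unresolved grade 3 or greater rise still counts in Cycle 1.
- *That earlier studies show the event is likely here.* Section 2.2.2.2 gives neither grade nor symptoms for the creatinine DLTs. C15005 used other schedules, and C15001 pooled four, with starting doses up to 147 mg/m² against 20-59 mg/m² for the escalation levels here. The closest study by disease, C15003, lists renal failure, a clinical diagnosis that may fall outside footnote G.

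**Conclusion.** The gap is real and modest. On the text, no rule requires the remaining in-cycle doses to be held for a related, asymptomatic grade 3-4 creatinine increase, in any cycle. The exposures in the working describe what could be given if the event occurs and the investigator continues. They say nothing about how often that happens. The documents put increased creatinine in the 20%-or-less column for both drugs (n = 474 and n = 583) without a split by grade, so the event is probably uncommon and its rate cannot be computed.

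The coagulation case is secondary. It is confined to Cycle 1 Day 5 or shifted doses, and increased INR appears only on belinostat's insufficient-evidence list.

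The conclusion rests on two readings: that footnote G applies to the whole catch-all row, and that its term carries the meaning given in 7.2.1 and at the head of 7.2.2. An amendment is worthwhile because the present wording lifts a hold that the row would otherwise impose, and the tests needed are already scheduled.

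**What to change.** - **Footnote G:** add grade 3 or greater creatinine increase, and grade 3 or greater PT/INR/aPTT prolongation off anticoagulation, to the exceptions for omission or delay only. Keep the row's thresholds: after grade 3, to grade 1 or less or tolerable grade 2; after grade 4, to below grade 2; or to baseline. A stricter threshold would treat an asymptomatic laboratory value more severely than a symptomatic grade 3 toxicity. Leave dose reduction on resumption to the investigator with the PI.
- **Study calendar:** require creatinine to be read before dosing on the days it is already scheduled.
- **Footnote F:** state that for these laboratory-only holds the 14-day discontinuation clock runs from the planned start of the next cycle, as in Section 7.3. Otherwise the new hold could end therapy around Day 17. The matching 14-day line in 7.2.1 should agree.

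No new tests are needed, and regular re-evaluation during a delay is already required by 7.2.1. The cost is same-day results, a few doses delayed or omitted for laboratory-only events, and occasionally a patient who is not evaluable for DLT and must be replaced, in the situations listed in step 4 of the working.
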